10.4.3. Treatment Phases (Concomitant Medications)

Concomitant medications will be classified according to time of occurrence relative to the first and last dose of mepolizumab within specific study parts.

Treatment/Study Phase	Definition
Taken Before the Run-in	If Con-med Start Date < Date of Visit 1
Taken During the Run-in	
 If Con-med Start Date < Date of Visit 1 and Con-med Stop Date ≥ Date of Visit 1, or If Date of Visit 1 ≤ Con-med Start Date < First Part A dose of mepolizumab
Taken During Treatment (Part A)	
 If Con-med Start Date < First Part A dose of mepolizumab and Con-med Stop Date ≥ First Part A dose of mepolizumab, or If First Part A dose of mepolizumab ≤ Con-med Start Date ≤ Last Part A dose of mepolizumab + 28 days If the con-med start or stop date is missing or partial then the con-med will be considered on-treatment unless there is evidence to the contrary (e.g. month/year of con-med stop date is present and is before the month/year of the first Part A dose of mepolizumab).
Started During Treatment (Part A)	Subset of con-meds Taken During Treatment (Part A) for which: First Part A dose of mepolizumab ≤ Con-med Start Date ≤ Last Part A dose of mepolizumab + 28 days
Taken Post Treatment (Part A)	
 Con-med Stop Date > Last Part A dose of mepolizumab + 28 days
Taken During Treatment (Part B)	
 If Con-med Start Date < First Part B dose of mepolizumab and Con-med Stop Date ≥ First Part B dose of mepolizumab, or If First Part B dose of mepolizumab ≤ Con-med Start Date ≤ Last Part B dose of mepolizumab + 28 days If the con-med start or stop date is missing or partial then the con-med will be considered on-treatment unless there is evidence to the contrary (e.g. month/year of con-med stop date is present and is before the month/year of the first Part B dose of mepolizumab).
Started During Treatment (Part B)	Subset of con-meds Taken During Treatment (Part B) for which: First Part B dose of mepolizumab ≤ Con-med Start Date ≤ Last Part B dose of mepolizumab + 28 days
Taken Post Treatment (Part B)	
 Con-med Stop Date > Last Part B dose of mepolizumab + 28 days
Time Since 1 st Dose (Days)*	If Treatment Start Date > Con-med Start Date = Con-med Start Date - First Part A dose of mepolizumab If Treatment Start Date ≤ Con-med Start Date = Con-med Start Date - First Part A dose of mepolizumab + 1 If Treatment Start Date or Con-med Start Date is missing = missing.
Duration (Days)	Con-med Stop Date - Con-med Start Date + 1
* Note: will be derived as time since 1 st dose of mepolizumab utilising the First Part A dose of mepolizumab for both study parts A and B	

A medication will be summarised in every treatment/study phase in which it was taken, so for example a medication that was started in the run-in and stopped during treatment will appear in both the during the run-in and during treatment tables

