10.3.2. Part A Data Cut Date

When reporting study Part A, a data cut date will be applied to all data collected within the Case Report Form (CRF) prior to SDTM conversion. This cut date subset the data to only those assessments/visits prior to the last subject completing the Visit 8 (Week 20) visit date (LSLV Part A).

All external vendor data (e.g. Labs, ECGs, Immunogenicity) will not be possible to subset and therefore data will be present within the SDTM datasets past this data cut date.

When creating ADaM datasets all dates beyond this applied data cut date will be removed and will be documented clearly within the ADaM dataset metadata.

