10.4. Appendix 4: Treatment Phases

10.4.1. Treatment Phases (Adverse Events)

Adverse events will be classified according to time of occurrence relative to the first and last dose of mepolizumab within specific study parts.

Treatment Phase	Definition
Pre-Treatment	AE Onset Date & time < First Part A dose of mepolizumab If mepolizumab treatment is never started then all AEs will be classified as pre-treatment.
On-Treatment (Part A)	First Part A dose of mepolizumab ≤ AE Onset Date & time ≤ Last Part A dose of mepolizumab + 28 days If an AE start date is missing or partial then the AE will be considered on-treatment unless there is evidence to the contrary (e.g. month/year of onset date is present and is earlier than the month/year of First Part A dose of mepolizumab).
Post-treatment (Part A)	For subjects entering Part B: Last Part A dose of mepolizumab + 28 days < AE Onset Date & time < First dose of Part B mepolizumab For subjects not entering Part B: Last Part A dose of mepolizumab + 28 days < AE Onset Date & time ≤ Visit 8 (Week 20) visit date
On-Treatment (Part B)	First dose of Part B mepolizumab ≤ AE Onset Date & time ≤ Last Part B dose of mepolizumab + 28 days If an AE start date is missing or partial then the AE will be considered on-treatment unless there is evidence to the contrary (e.g. month/year of onset date is present and is earlier than the month/year of First Part B dose of mepolizumab).
Post-treatment (Part B)	AE Onset Date & time > Last Part B dose of mepolizumab + 28 days
Onset Time Since 1 st Dose (Days)*	If Treatment Start Date > AE Onset Date = AE Onset Date - First Part A dose of mepolizumab If Treatment Start Date ≤ AE Onset Date = AE Onset Date - First Part A dose of mepolizumab + 1 If Treatment Start Date or AE Onset Date is missing = missing.
Duration (Days)	AE Resolution Date – AE Onset Date + 1
Drug-related	If relationship is marked 'YES' on Inform/eCRF OR value is missing.
* Note: will be derived as time since 1 st dose of mepolizumab utilising the First Part A dose of mepolizumab for both study parts A and B	

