10.4.2. Treatment Phases (Exacerbations)

Exacerbation data will be classified according to time of occurrence/assessment relative to the first and last dose of mepolizumab and the participation of subjects within to specific study parts (as dictated by attendance dates of specific visits).

Treatment Phase	Definition
Pre-Treatment	Exacerbation Onset Date & time < First Part A dose of mepolizumab If mepolizumab treatment is never started then all exacerbations will be classified as pre-treatment.
On-Treatment (Part A)	Subjects completing Part A: First Part A dose of mepolizumab ≤ Exacerbation Onset Date & time ≤ Visit 6 (Week 12) visit date Subjects discontinuing study treatment/withdrawing early from Part A: First Part A dose of mepolizumab ≤ Exacerbation Onset Date & time ≤ Earliest of (1) Last Part A dose of mepolizumab + 28 days or (2) Early Withdrawal visit date
Post-treatment (Part A)	Subjects completing Part A and entering Part B: Visit 6 (Week 12) visit date < Exacerbation Onset Date & time < First dose of Part B mepolizumab Subjects completing Part A and not entering Part B: Visit 6 (Week 12) visit date < Exacerbation Onset Date & time ≤ Visit 8 (Week 20) visit date Subjects discontinuing study treatment/withdrawing early from Part A: Earliest of (1) Last Part A dose of mepolizumab + 28 days or (2) Early Withdrawal visit date < Exacerbation Onset Date & time ≤ Visit 8 (Week 20) visit date
On-Treatment (Part B)	Subjects completing Part B: First Part B dose of mepolizumab ≤ Exacerbation Onset Date & time ≤ Visit 22 (Week 72) visit date Subjects discontinuing study treatment/withdrawing early from Part B: First Part B dose of mepolizumab ≤ Exacerbation Onset Date & time ≤ Earliest of (1) Last Part B dose of mepolizumab + 28 days or (2) Early Withdrawal visit date
Post-treatment (Part B)	Subjects completing Part B: Exacerbation Onset Date & time > Visit 22 (Week 72) visit date Subjects discontinuing study treatment/withdrawing early from Part B: Exacerbation Onset Date & time > Earliest of (1) Last Part B dose of mepolizumab + 28 days or (2) Early Withdrawal visit date

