1.17.	Safety		Summary of Asthma Concomitant Medication Taken Before the Run-In by Respiratory Medication Class (Part A)	See format of Study Population Table 1.21 (200862 'final' reporting effort)	SAC1
1.18.	Safety		Summary of Asthma Concomitant Medication During the Run-In by Respiratory Medication Class (Part A)	See format of Study Population Table 1.22 (200862 'final' reporting effort)	SAC1

Study Population Tables					
No.	Population	IDSL / TST ID / Example Shell	Title	Programming Notes	Deliverable Priority
1.19.	Safety		Summary of Asthma Concomitant Medication Taken During Treatment by Respiratory Medication Class (Part A)	See format of Study Population Table 1.23 (200862 'final' reporting effort)	SAC1
1.20.	Safety		Summary of Asthma Concomitant Medication Taken Post-Treatment by Respiratory Medication Class (Part A)	See format of Study Population Table 1.25 (200862 'final' reporting effort)	SAC1
1.21.	Safety	CM1	Summary of non-Asthma Concomitant Medication Taken During Treatment (Part A)		SAC1
Protocol Deviations					
1.22.	Safety	DV1B	Summary of Important Protocol Deviations (Part A)		SAC1

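### The SAP's Part A post-treatment rule for concomitant medications has no upper bound, so medications started in Part B can enter Table 1.20

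*SAP*

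**What the plan says.** SAP 10.4.3 defines the Part A post-treatment phase for concomitant medications by the stop date alone: "Con-med Stop Date > Last Part A dose of mepolizumab + 28 days". Below that table it states the principle for medications that span phases: "A medication will be summarised in every treatment/study phase in which it was taken".

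The other two sections of the same appendix close the phase for a child who continues. For adverse events, 10.4.1 has "Last Part A dose of mepolizumab + 28 days < AE Onset Date & time < First dose of Part B mepolizumab". For exacerbations, 10.4.2 has "Visit 6 (Week 12) visit date < Exacerbation Onset Date & time < First dose of Part B mepolizumab". For children who do not continue, both end at the Visit 8 date.

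The affected display is Table 1.20 in SAP 10.10.2.1, which summarises post-treatment asthma medication in Part A by respiratory medication class. SAP 10.3.2 limits the case report form data for the Part A report to assessments and visits "prior to the last subject completing the Visit 8". Under SAP 3.1 and 3.2 the Part A outputs are final and are not rerun with Part B.

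**The concern.** The Part A post-treatment phase is the interval from about Week 12 to Week 20, when children are off mepolizumab. Table 1.20 is the display that should describe their asthma medication in that interval. A rule that asks only whether a medication stopped after Week 12 also admits a short course, such as oral steroids, both started and stopped after dosing resumed in Part B. The same record also meets the Part B during-treatment rule, "If First Part B dose of mepolizumab ≤ Con-med Start Date ≤ Last Part B dose of mepolizumab + 28 days". Table 1.20 could then mix off-drug use with use during renewed treatment, and no planned rerun would correct it.

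**Working it through.** No sample size or error rate is involved, so the check is one of logic.

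**1. The three Part A post-treatment rules side by side**

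| Data | SAP section | Starts after | Ends, child entering Part B | Ends, child not entering Part B |
|---|---|---|---|---|
| Adverse events | 10.4.1 | last Part A dose + 28 days | first Part B dose | Visit 8 |
| Exacerbations (Part A completers) | 10.4.2 | Visit 6 | first Part B dose | Visit 8 |
| Concomitant medications | 10.4.3 | stop date after last Part A dose + 28 days | no bound | no bound |

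Only the medication row is open.

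**2. The rule applied to test records**

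The timing is nominal, in days since the first Part A dose (Time and Events tables):
- last Part A dose, Week 8: 8 × 7 = 56; plus 28 gives day 84 (Week 12)
- first Part B dose, Week 20: 20 × 7 = 140
- last Part B dose, Week 68: 68 × 7 = 476; plus 28 gives day 504 (Week 72)

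| Medication taken (days) | Phases under the rule as written | Phases if start must precede day 140 |
|---|---|---|
| 100 to 110 | Post A | Post A |
| 200 to 207 | Post A, During B | During B |
| 280 to 287 | Post A, During B | During B |
| 400, ongoing, no stop date | During B | During B |
| 510 to 515 | Post A, Post B | Post B |
| −30 to 600 | During A, Post A, During B, Post B | unchanged |

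Three of these records began only after Part B dosing started, yet are labelled Part A post-treatment. The added start-date condition removes exactly those three. It leaves the genuine off-drug course and the long-running medication where the SAP's principle puts them.

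**3. Whether the data cut removes the error**

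The cut falls when the last child reaches Week 20. A child first dosed E weeks earlier is then at Week 20 + E. Visit 9 takes place on the same day as Visit 8 (SAP 10.3.1), so that child has (20 + E) − 20 = E weeks of Part B records inside the cut. The limit is the 60 weeks from Week 20 to Week 80.

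The documents give no accrual span, so E is an assumption: E = 4, 12, 26 or 52 gives about 4, 12, 26 or 52 weeks. The day 200 to 207 course ends (207 − 140)/7 = 9.6 weeks into Part B, so it falls inside the cut once E is about 10 weeks or more. The cut limits the spill but does not remove it.

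**The case against.** **Intent is clear, and a careful programmer would follow it.** The principle under the 10.4.3 table states the intent, and the table title says Part A. That is fair, but the row is the operative rule, and coding it as written contradicts the principle. SAP 10.3.1 does attribute spontaneous events to a single study part. It gives adverse events, exacerbations and unscheduled visits as examples, not medications, and forcing a medication into one part would conflict with the multi-phase principle.

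**Little depends on the table.** This largely stands. Table 1.20 is descriptive and the study tests no hypothesis. Exacerbations from Week 0 to Week 20, including those treated with steroids, are summarised separately under a correctly bounded rule. The spill needs a recorded stop date before the cut. If the table counts children within a class, a child already using that class in Weeks 12 to 20 adds nothing. The table's format is taken from another study's reporting effort, which is not available here. A reader might divide weeks of Part B records by the 8-week window and call the ratio the inflation. It is not: it compares follow-up time, not counts by medication class.

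**A stronger reading concerns adverse events.** SAP 10.4.1 repeats one default in both on-treatment rows: "If an AE start date is missing or partial then the AE will be considered on-treatment unless there is evidence to the contrary". A reader might infer that events with partial dates are counted in both parts and inflate the Part B primary safety endpoint. The documents do not support this:
- The partial dates described in 10.7.2.1 give month and year. The two on-treatment windows are nominally 140 − 84 = 56 days apart, so no calendar month touches both, and a known month is evidence against at least one part.
- Partial dates are also queried and, if unresolved, imputed to a single date.
- Only an event with no year at all after query meets both defaults. No size can be put on that from the 28 children planned for Part A treatment, because the size of Part B is not fixed and a child with another Part B event would not change incidence.

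**Conclusion.** The medication rule in SAP 10.4.3 is wrong as written. It omits a bound that the same appendix applies to adverse events and exacerbations, and neither the part-attribution rule nor the data cut supplies it. Table 1.20 could therefore include medication started after Part B dosing began.

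The effect is confined to that descriptive table. It requires a child enrolled before the last one and a medication started and stopped in Part B before the cut. The exposure is about E weeks of Part B records per such child, with E unknown. The change in the table's counts cannot be computed from the documents. No primary or secondary endpoint is affected. The finding does not extend to double counting of partially dated adverse events.

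**What to change.** Replace the Part A post-treatment row in SAP 10.4.3 with two conditions, both required:
- the start date is before the first Part B dose or, for a child not entering Part B, on or before the Visit 8 date; and
- the stop date is after the last Part A dose plus 28 days, or the medication is ongoing.

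The ongoing clause is needed because the present row relies on a stop date and does not say how a medication without one is treated.

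One small residual would remain. Under 10.7.2.1 a partial start date is moved to the earliest possible date, so a medication whose start is known only to the month in which Part B dosing began would usually still be admitted. That follows the SAP's existing convention.

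The cost is one row of Appendix 4 and a small program change before the Part A outputs are produced. It needs no new data and no protocol amendment.

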10.5. Appendix 5: Data Display Standards & Handling Conventions

10.5.1. Study Treatment & Display Descriptors

For all displays subjects will be presented in the treatment group received during the study.

10.5.1.1. Part A

All displays will be presented by mepolizumab dose group within Part A (Mepolizumab 40 mg and 100mg SC) and overall, when appropriate.

Treatment Group Descriptions			
RandAll NG ^[1]		Data Displays for Reporting	
Code	Description	Description ^[3]	Order ^[2]
N/A	N/A	Mepolizumab 40 mg SC	1
		Mepolizumab 100 mg SC	2
		Mepolizumab SC	3

NOTES:

1. This is not a randomised study and treatment group descriptions are not required for RandAll NG
2. Order represents treatments being presented in TFL, as appropriate.
3. 'Mepolizumab SC' group includes all subjects who received at least one dose of mepolizumab regardless of dose.

10.5.1.2. Part B

All displays will be presented by mepolizumab dose group within Part B and overall.

Note: Subjects which are switched from 40mg to 100mg SC during Part B will be presented separately [Mepolizumab 40/100 mg SC].

Treatment Group Descriptions			
RandAll NG ^[1]		Data Displays for Reporting	
Code	Description	Description ^[3]	Order ^[2]
N/A	N/A	Mepolizumab 40 mg SC	1
		Mepolizumab 100 mg SC	2
		Mepolizumab 40/100 mg SC	3
		Mepolizumab SC	4

NOTES:

1. This is not a randomised study and treatment group descriptions are not required for RandAll NG
2. Order represents treatments being presented in TFL, as appropriate.
3. 'Mepolizumab SC' group includes all subjects who received at least one dose of mepolizumab regardless of dose.

10.5.2. Baseline Definition & Derivations**10.5.2.1. Definition of Baseline**

- The baseline value for each assessment will be the latest value recorded prior to the first dose of mepolizumab.
- If an assessment was performed on the same day as the first dose of study treatment but it is known that the assessment was done after administration of treatment (i.e. because time of assessment is available and is after time of first dose) then this value will not be used as the baseline value.
- The same baseline definition (latest value recorded prior to the first dose of mepolizumab in Part A) will be used in the analyses of both Part A and Part B data.

10.5.2.2. Derivations of Change from Baseline Data

Definition	Reporting Details
Change from Baseline	= Post-Dose Visit Value – Baseline
Ratio to baseline	= Post-Dose Visit Value / Baseline
Maximum Change from Baseline	= Highest Post-Dose Value - Baseline

NOTES :

- Unless otherwise specified, the baseline definitions specified in Section 10.5.2.1 will be used for derivations for endpoints / parameters and indicated on summaries and listings.
- The baseline definition will be footnoted on all change from baseline displays.

10.5.3. Reporting Process & Standards

Reporting Process	
Software	
The currently supported versions of SAS software will be used to perform all data analyses, generate tables, figures and listings.	
Reporting Area (Part A)	
HARP Server	: UK1SAL00175
HARP Area	: /arenv/arprod/sb240563/mid200363/part_a
Quality Control (QC) Spread sheet	: /arenv/arwork/sb240563/mid200363/part_a/document
Reporting Area (Part B)	
HARP Server	: UK1SAL00175
HARP Area	: /arenv/arprod/sb240563/mid200363/final
Quality Control (QC) Spread sheet	: /arenv/arwork/sb240563/mid200363/final/document

Reporting Process
Analysis Datasets

 • Analysis datasets will be created according to CDISC standards (current versions of SDTM IG & ADaM IG). • For creation of ADaM datasets (ADCM/ADAE), the same version of dictionary datasets will be implemented for conversion from SI to SDTM.
Generation of RTF Files

 • RTF files will be generated only for summary tables

Reporting Standards
General

 • The current GSK Integrated Data Standards Library (IDSL) will be applied for reporting, unless otherwise stated: 
 ○ 4.03 to 4.23: General Principles ○ 5.01 to 5.08: Principles Related to Data Listings ○ 6.01 to 6.11: Principles Related to Summary Tables ○ 7.01 to 7.13: Principles Related to Graphics
Formats

 • All data will be reported according to the actual treatment the subject received (see Section 10.5.1). • The reported precision of data will follow the IDSL statistical principles but may be adjusted to a clinically interpretable number of decimal places.
Planned and Actual Time

 • Reporting for tables and figures : 
 • Nominal visits (planned time relative to dosing) will be used in summary figures and summary tables. Actual time relative to dosing will be used in individual subject figures. • The impact of any major deviation from the planned assessment times and/or scheduled visit days on the analyses and interpretation of the results will be assessed as appropriate. • Reporting for Data Listings: 
 • Planned and actual time relative to study drug dosing will be shown in listings (Refer to IDSL Statistical Principle 5.05.1). • Unscheduled or unplanned readings will be presented within the subject data listings • Scheduled visits outside the protocol defined time-windows (i.e. recorded as protocol deviations) will be included in listings, summaries and statistical analyses. The impact of any major deviation from the planned assessment times and/or scheduled visit days on the summaries, figures, analyses will be assessed as appropriate.
Unscheduled Visits

 • When possible unscheduled assessments will be slotted to the closest adjacent scheduled visit. If an unscheduled visit occurs between two completed scheduled visits, the data from the unscheduled visit will not be used in summary tables which are based on by-visit assessments. The information from the unscheduled visit will be included in 'any time post-baseline' summaries and will also be presented in any relevant listings. See Section 10.3 for further details.

Reporting Standards	
Descriptive Summary Statistics	
Continuous Data	Refer to IDSL Statistical Principle 6.06.1
Categorical Data	N (number of subjects in the treatment group), n (number of subjects with non-missing values), frequency, %
Reporting of Pharmacokinetic Concentration Data	
Descriptive Summary Statistics	Refer to IDSL Statistical Principle 6.06.1 Refer to GUI_51487 for further details of handling NQ/BQL values
Reporting of Pharmacokinetic Parameters	
Descriptive Summary Statistics	The following summary statistics will be presented for all parameters: N, n, mean, median, SD, min and max In addition the following summary statistics will be presented for all parameters with the exception of t1/2. N, n, geometric mean, 95% CI of geometric mean, standard deviation (SD) of logged data and [between] geometric coefficient of variation (CV _b (%)) will be reported. [1] $CV_b (\%) = \sqrt{(\exp(SD^2) - 1) * 100}$ (SD = SD of log transformed data)
Reporting of Blood Eosinophil Count	
Descriptive Summary Statistics	The following summary statistics will be presented for blood eosinophil count: N, n, geometric mean, 95% CI of geometric mean, SD (natural log scale), median, min and max
Graphical Displays	

 Refer to IDSL Statistical Principals 7.01 to 7.13. 	

